3.2 Background and Significance

VTE is a known potential complication of malignancy and is particularly common among women with epithelial ovarian cancer (EOC).^[1,2] In addition to having active cancer, women with EOC are predisposed to other well-established risk factors for VTE, including impaired mobility, increasing age, and advanced disease.^[3] The risk of VTE is even greater among patients with clear cell histology, thrombocytosis, high grade tumors, and co-morbid cardiovascular risk factors (e.g., obesity, hypertension, diabetes).^[4-7] In a recent study at our institution, we found that women with advanced ovarian cancer receiving NACT are at high risk for VTE with an incidence of nearly 8%.^[8]

Importantly, the occurrence of VTE among patients with EOC is associated with increased morbidity, decreased survival, and increased healthcare costs.^[9-11] Timely interval debulking surgery and the ability to achieve of optimal surgical debulking also remain critical components of care for advanced EOC. In the aforementioned study, we observed that the average time from start of NACT to interval debulking surgery was longer for patients who experienced a VTE during NACT as compared to those who had not; these patients were also less likely to have their disease optimally debulked at the time of interval surgery. The high incidence of VTE during NACT reported in our study as well as the associated morbidity contributes to a growing body of evidence suggesting that thromboprophylaxis during NACT is warranted.

According to the current guidelines from the American Society of Clinical Oncology, thromboprophylaxis with either apixaban, rivaroxaban, or low molecular weight heparin (LMWH) is recommended for high risk ambulatory cancer patients (defined as a Khorana score greater than or equal to 2) receiving systemic chemotherapy. Patients with a primary gynecologic malignancy receive one point in the Khorana score at baseline, and the majority of ovarian cancer patients would meet criteria for an additional point. High risk Khorana scores defined as 3 or greater have a 6.7-7.1% risk of VTE which is similar to the incidence defined in the previously described study of patients receiving NACT for advanced EOC. These patients are therefore considered high risk for adverse thromboembolic events when initiating systemic chemotherapy.

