8.7.2. Statistical Hypothesis, Model, and Method of Analysis

The goal for initiating accrual into this study will be September 1st, 2020. Patients will continue to be enrolled through December 30th, 2021. Subjects will be followed through the primary NACT treatment course until interval debulking surgery, with an estimated duration of 6-9 months following enrollment depending on the number of NACT cycles the individual undergoes. The primary efficacy outcome of this study is rate of VTE among the study cohort during NACT. The primary safety outcome is the incidence of clinically significant adverse drug events. Data from medication adherence diaries and AE symptom questionnaires will be reviewed and entered into the REDCap database. An intention-to-treat analysis will be performed. Subjects withdrawn due to medication intolerance or adverse drug events will be censored, and the research team will continue to collect clinical data for the predetermined follow up period.

We will calculate the incidence of VTE during the study period defined above (enrollment to interval debulking surgery or 1 week after completion of the primary neoadjuvant chemotherapy course if debulking surgery is deferred) and estimate a 95% exact binomial confidence interval. Since this is a pilot study, the incidence of venous thromboembolism in the study population will be compared to a historical control from a previous research study

of the incidence of venous thromboembolism among women receiving neoadjuvant chemotherapy for advanced ovarian cancer in which the majority of patients were from Duke. A drop greater than 20% (from approximately 8% to 6.4%) in the rate of venous thromboembolism would be considered clinically meaningful. If the true VTE rate is 6.4%, the width of the 95% exact binomial confidence interval will be 0.098. We will also monitor for adverse safety events related to low dose aspirin use, including major or minor bleeding events, gastrointestinal complications, and medication intolerance (side effects or adverse reaction). Further detail regarding AE monitoring and reporting is outlined in a previous section.

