13.6 Sample Size Calculation

Sample size calculation is not applicable to this study. Since this is a pilot investigation, the incidence of venous thromboembolism in the study population will be compared to a historical control from a previous research study of the incidence of venous thromboembolism among women receiving neoadjuvant chemotherapy for advanced ovarian cancer in which the majority of patients were from Duke. A drop greater than 20% (from approximately 8% to 6.4%) in the rate of venous thromboembolism would be considered clinically meaningful.

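### The comparison of the trial's VTE rate with the historical 8% carries only one of its two sources of sampling error

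*Combined protocol and SAP*

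**What the plan says.** The statistical methods section (printed as 8.7.2, listed in the contents as 13.4.2) says that the trial's VTE incidence will be "compared to a historical control from a previous research study", a study of "neoadjuvant chemotherapy for advanced ovarian cancer in which the majority of patients were from Duke". It then sets the size of effect of interest: "A drop greater than 20% (from approximately 8% to 6.4%) in the rate of venous thromboembolism would be considered clinically meaningful".

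The inferential content is confined to the trial arm. The team will calculate the incidence and "estimate a 95% exact binomial confidence interval". Its precision is given as follows: "If the true VTE rate is 6.4%, the width of the 95% exact binomial confidence interval will be 0.098".

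The source of the 8% is Section 3.2, which reports from the institution's own recent study (reference 8) that women "receiving NACT are at high risk for VTE with an incidence of nearly 8" percent. Sections 5.1 and 5.3 repeat that figure. Section 13.6 repeats that "the incidence of venous thromboembolism in the study population will be compared to a historical control" and adds no method. Nowhere do the documents give the historical number of events, number of patients or confidence interval, and nowhere do they name a two-sample interval or test.

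**The concern.** A statement that aspirin lowered the VTE rate is a statement about a difference between two estimated rates. Its uncertainty has two parts: the sampling error of the trial and that of the earlier study. The plan quantifies the first and is silent on the second, so in effect 8% serves as an exact benchmark.

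The effect of interest is only 1.6 percentage points (8% minus 6.4%). If the benchmark's own error is of that order or larger, a reader who lays the trial's interval beside a bare 8% will think the comparison more precise than it is, and will see an apparent benefit or harm too often.

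**Working it through.** **Inputs.** Trial N: 60 at Duke plus 60 at the added site = 120 (Sections 7.1 and 10). Historical rate 8%, threshold 6.4% (Section 8.7.2). The historical sample size m is not in the documents; m = 100, 200 and 400 are assumed.

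**1. The plan's own figure.** 0.064 × 120 = 7.68, rounded to 8 events. The Clopper-Pearson interval for 8/120 is 2.92% to 12.71%, width 0.0979. This reproduces 0.098. With N=60 and 4 events the width would be 0.1435, so the stated figure belongs to N=120 and reflects the trial arm alone.

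**2. What is left out.** Variance of the difference = 0.064 × 0.936/120 + 0.08 × 0.92/m. The first term is 0.000499 (SE 2.23 points). The second is 0.000736, 0.000368 or 0.000184.

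| Assumed m | SE of difference (points) | Trial arm's share of variance | Exact 95% CI for an observed 8% |
|---|---|---|---|
| 100 | 3.51 | 40% | 3.5-15.2% |
| 200 | 2.94 | 58% | 4.6-12.7% |
| 400 | 2.61 | 73% | 5.5-11.1% |

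The 6.4% threshold lies inside every interval in the last column.

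**3. A two-sample interval.** Newcombe 95% interval for 6.4% (N=120) minus 8% (m). For m=200 the Wilson limits are 3.23% to 12.27% for the trial and 4.98% to 12.60% for the historical rate, so:
- lower limit = −1.6 − √[(6.40−3.23)² + (12.60−8.00)²] = −7.2 points
- upper limit = −1.6 + √[(12.27−6.40)² + (8.00−4.98)²] = +5.0 points

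The same formula gives −9.3 to +5.4 for m=100 and −6.0 to +4.7 for m=400.

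**4. Reading the planned interval against the historical estimate.** Let both true rates be 8%. Sum the binomial probabilities over all trial counts (N=120) and historical counts (m) for which the trial's exact 95% interval excludes the observed historical rate.

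| Benchmark | Excluded in either direction | Trial interval wholly below (false benefit) |
|---|---|---|
| 8% known exactly | 2.6% | 1.1% |
| Estimated, m=400 | 6.4% | 2.7% |
| Estimated, m=200 | 9.7% | 3.8% |
| Estimated, m=100 | 16.3% | 6.4% |

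**5. What the trial could show with a perfect benchmark.** The upper exact limit is below 8% only with 3 or fewer events in 120 (3/120 gives 7.13%, 4/120 gives 8.31%). The probability of that is 4.7% if the true rate is 6.4%.

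**The case against.** The strongest reply is that this is a self-described pilot with no sample size calculation, no test and no alpha for the comparison. Step 5 supports it: even a perfectly known 8% would leave the trial unable to distinguish 6.4% from 8%, so adding historical error widens an interval that is already inconclusive. The exact interval is also conservative. At m=400 the false-benefit rate is 2.7%, close to the nominal 2.5%. All of this stands, and it limits the importance of the point. It does not remove it, because efficacy is still a primary objective and the plan still names a numerical drop as meaningful.

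Three stronger readings are tempting, and the documents do not support them:
- **That exactly half of the sampling error is missing.** The share cannot be derived without m. Half of the variance would be missing only if m were about 147.
- **That the plan tests against a fixed 8%.** It names no test. Error rates of about 19%, 12% and 9% (m = 100, 200, 400) would apply to a two-sided normal-approximation test, which is not in the plan. The figures in step 4 use the interval that is.
- **That efficacy will be claimed if the observed rate is below 6.4%.** The text gives 6.4% as a threshold of clinical relevance and attaches no decision rule to it.

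It can also be said that a formal two-sample interval lends rigour to a comparison of unlike populations. Eligibility is now restricted to a Khorana score of 1, while the 8% is reported with no stated score restriction. That is a fair caution and a reason to accept a purely descriptive comparison as an alternative.

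**Conclusion.** The point holds: the efficacy comparison, as planned, reflects the trial's sampling error and not the historical study's, and the 0.098 width therefore understates the uncertainty of the comparison. By how much depends on an unstated number. Under assumed historical sizes of 100 to 400, the trial's interval would exclude the observed historical rate 16% down to 6% of the time when nothing differs (false benefit 6.4% down to 2.7%), against 2.6% (1.1%) with a known benchmark. These figures assume N=120 analysed, a common true rate of 8%, and a reader who lays the planned interval against the historical estimate; the plan does not prescribe that reading.

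The consequence is for how honestly the comparison is reported, since no realistic result near 6.4% would be conclusive either way. It is a worthwhile and inexpensive correction, not a flaw that invalidates the pilot.

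**What to change.** In Section 13.4.2 (printed 8.7.2):
- State the number of VTE events, the number of patients and the exact 95% interval from the earlier study. It is the institution's own, so the counts should be obtainable.
- Report the difference in proportions, trial minus historical, with a 95% interval that uses both samples (Newcombe or Miettinen-Nurminen), and base any efficacy statement on that interval.
- Alternatively, say plainly that the comparison is descriptive and that no efficacy conclusion will be drawn from it.

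The cost is a few sentences and one calculation, with no change to patients, visits or treatment. The downside is a wider reported interval. Neither option cures the separate difference in Khorana score between the trial and the historical population, which needs its own treatment.

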8.7.3. Handling of missing values, censoring, and discontinuations

An intention-to-treat analysis will be performed for all enrolled subjects. Due to the small sample size, we will not impute missing data. If a participant is censored due to the occurrence of a VTE or a significant AE, the study team will continue to collect clinical data until the predetermined follow up period is complete.

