DOAC instead. Any existing patients with a Khorana score of more than 1 who have already completed their aspirin regimen and are considered "on follow up" will remain on study.

Once enrolled in the study, subjects will receive a 30-day supply of low dose aspirin from a study team member and will be instructed to start taking one 81 mg tablet daily starting the first day of their first neoadjuvant chemotherapy cycle. Subjects may also be consented after the first day of their first cycle so long as they are taking the aspirin by the end of the day of their second cycle. Patients who are already on low dose aspirin for another indication will still be eligible for the study but will be instructed to take the study drug such that adherence can be monitored. These patients will continue their prior regimen following completion of NACT. Participants will be instructed to complete medication adherence diaries and AE symptom questionnaires. At each subsequent clinic visit for consideration of an additional NACT cycle, a member of the research team will review medication adherence diaries and AE symptom questionnaires and administer the Voils DOSE-Nonadherence measure survey. If symptoms are concerning for a potential AE, the research team personnel will inquire further and discuss with the PI. Please see subsequent sections related to AE monitoring and reporting. No additional components of history and physical exam will be completed outside standard of care performed by the patient's provider prior to initiation of an additional cycle of NACT. Different patients may undergo different numbers of NACT cycles, and thus the 30-day supply of aspirin will be refilled by a member of the research team when the decision is made to proceed with an additional cycle.

Participants who experience clinically significant adverse drug events such as bleeding or medication intolerance will be withdrawn from the study. Subjects with significant chemotherapy-induced thrombocytopenia (platelet count less than 50,000) will be instructed to stop taking daily aspirin for 1 week until platelet counts normalize. If a subject withdraws from the study voluntarily, there will be no further follow up. If a participant is censored due to development of a VTE or clinically significant AE, the research team will continue to collect clinical data until the end of the predetermined follow up period.

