The primary selection criterion is a Khorana score of 1; additional criteria are detailed in a subsequent section. The Khorana score will be calculated according to the following parameters in closest proximity to the first cycle of chemotherapy: 1 point for gynecologic cancer, 1 point for BMI ≥ 35 , 1 point for Hgb < 10 or use of red blood cell growth factors, 1 point for leukocyte count $> 11,000$, and 1 point for platelets $\geq 350,000$. Patients therefore have a baseline Khorana score of 1 and are ineligible if any additional Khorana score parameters are met. Prior to the April 2021 amendment, Khorana score was not a part of the inclusion criteria. Any existing patient with a Khorana score of more than 1 who is receiving study drug at the time the amendment is approved will be contacted by the study PI to discuss switching to a DOAC. The patient will have the option to remain on study and complete their aspirin regimen or come off study and begin a DOAC instead. Any existing patients with a Khorana score of more than 1 who have already completed their aspirin regimen and are considered "on follow up" will remain on study.

An estimated 120 patients will receive neoadjuvant chemotherapy for advanced ovarian cancer at Duke Gynecology Oncology clinics for the designated study recruitment period of 09/01/2020 to 12/30/2021 with an estimated 50% accrual rate for a total of 60 enrolled patients. Sarasota Memorial Health Care System has been added as an additional site and plans to recruit an additional 60 subjects.

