7.4 Definition of Evaluable Subjects, On Study, and End of Study

Evaluable subjects are participants who are enrolled in the study, given the study drug (aspirin) and receiving NACT until interval debulking surgery.

On study participants are those who are receiving aspirin or who are censored due to VTE or AE but for whom clinical data is still being collected.

End of study is defined as one year from the investigation start date.

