Once enrolled in the study, subjects will receive a 30-day supply of low dose aspirin from the research team and will be instructed to start taking one 81 mg tablet daily starting the first day of their first NACT cycle. Subjects may also be consented after the first day of their first cycle so long as they are taking the aspirin by the end of the day of their second cycle. Subjects will continue taking aspirin until the day of their interval debulking surgery unless previously on low dose aspirin for an alternative indication, in which case they will continue as directed by the prescribing physician. Patients will be instructed to complete medication adherence diaries and AE symptom questionnaires. At each subsequent clinic visit for consideration of an additional NACT cycle, a member of the research team will review medication adherence diaries and AE symptom questionnaires. If symptoms are concerning for a potential AE, the research team personnel will inquire further and discuss with the PI. Please see subsequent sections related to AE monitoring and reporting. No additional components of history and physical exam will be completed outside standard of care performed by the patient's provider prior to initiation of an additional cycle of NACT. Different patients may receive different numbers of cycles, and thus the 30-day supply of aspirin will be re-filled when the decision is made to proceed with an additional cycle.

This study will not impact standard of care treatment. The incidence of venous thromboembolism will be calculated from the study population and compared with a historical control. The incidence of adverse drug events will also be monitored and reported as detailed in a subsequent section.

Subjects will be followed as described above from the initiation of NACT and enrollment through interval debulking surgery unless they withdraw. There will be no additional monitoring in this follow up period with the exception of standard of care evaluation and documentation of the primary outcomes, including adverse drug events.

An outline of the trial procedures and assessments is detailed below:

	Treatment initiation						End of Study
--	----------------------	--	--	--	--	--	--------------

Phase	Screening	Cycle 1	Cycle 2	Cycle 3	Cycle 4	Cycle 5	Cycle 6	Follow-up (interval debulking surgery or completion of NACT)
Obtain Informed Consent	X							
Vital Signs	X	X	X	X	X	X	X	X
Height	X	X						
Weight, BP, Pulse	X	X	X	X	X	X	X	X

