6.6.2. Follow-up Requirements for Early Withdrawal

When subjects withdraw from the study, whether voluntarily or due to adverse drug events, they will continue to receive standard of care treatment at the discretion of their Gynecology Oncology provider and will continue to be followed accordingly. Since no other method of thromboprophylaxis is routinely implemented during NACT for ovarian cancer, subjects will not receive any other regimen. If subjects withdraw voluntarily, no additional follow up will be required. If subjects are withdrawn due to VTE occurrence of clinically significant AE, the study team will continue to collect clinical data until the predetermined follow up period is complete (interval debulking surgery or following completion of NACT, if no surgery).

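### VTE follow-up stops, or is not stated, after most exits from the study, yet the primary rate is taken over all enrolled subjects with no rule for unknown outcomes

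*Combined protocol and SAP*

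**What the plan says.** The numbering in the body is broken: headings 8.7.2 and 8.7.3 sit under Section 13.4, and 6.6.1 and 6.6.2 under Section 10.6.

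**Analysis.** Heading 8.7.3: "An intention-to-treat analysis will be performed for all enrolled subjects. Due to the small sample size, we will not impute missing data". Heading 8.7.2 defines the window as enrollment to interval debulking surgery, or one week after the end of chemotherapy if surgery is deferred. It specifies an incidence with a 95% exact binomial interval, compared with a historical rate of about 8%. A fall of more than 20%, to 6.4%, is called clinically meaningful.

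**Follow-up after an exit.**
- Adverse event or intolerance (8.7.2): "Subjects withdrawn due to medication intolerance or adverse drug events will be censored, and the research team will continue to collect clinical data". Sections 10.5, 8.7.3 and 6.6.2 say the same for a VTE or a significant AE.
- Voluntary withdrawal (3.3): "If a subject withdraws from the study voluntarily, there will be no further follow up". Heading 6.6.2 agrees: "If subjects withdraw voluntarily, no additional follow up will be required". Section 10 follows subjects "through interval debulking surgery unless they withdraw".
- Withdrawal by the investigator (6.6.1): the listed reasons include a Khorana score above 1, protocol deviation, administrative issues and disease progression. Continued data collection is stated only where the reason is an AE or a VTE.
- Switch to a DOAC (7.1): "The patient will have the option to remain on study and complete their aspirin regimen or come off study and begin a DOAC instead". Nothing is said about VTE follow-up afterwards.
- Section 7.4 counts as on study only "those who are receiving aspirin or who are censored due to VTE or AE but for whom clinical data is still being collected", so the other exits fall outside the definition.

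Section 10.5 anticipates no loss to follow-up, because the intervention is tied to receipt of chemotherapy. No withdrawal rate is given.

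**The concern.** A binomial proportion over all enrolled subjects has a fixed denominator, and the numerator is complete only if each subject's VTE status is known to the end of the window. Following the protocol exactly, status will be unknown for anyone who withdraws voluntarily, and probably for those who switch to a DOAC or are withdrawn for most non-AE reasons. The plan does not say whether such a subject is a non-event, is excluded, or is handled in some other way, so the choice could be made after the results are seen.

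Some exits may be related to risk. A Khorana score above 1 is a listed withdrawal reason and also the trigger for the DOAC option, and the background section treats a score of 2 or more as high risk. At stake is how far the single primary rate can be read against 8% in a study with no concurrent arm. Outcomes not collected during the study may also be hard to recover later.

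A smaller point concerns wording. Subjects who stop for an AE are called censored, a term that has no meaning for a binomial proportion. Their data are still collected, and the natural reading is that a later VTE counts.

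**Working it through.** **Inputs from the documents.** N = 60 + 60 = 120 planned subjects (7.1); historical rate 8%, meaningful rate 6.4%, difference 1.6 points (8.7.2); stated interval width 0.098 (8.7.2).

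**Assumptions (not in the documents).** True VTE risk 8% over the full window; constant hazard; leavers have the same risk as others and exit halfway; a share c = 5%, 10% or 20% is unfollowed.

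**Step 1: the plan's own figure.** 0.064 × 120 = 7.68, rounded to 8 events. The exact (Clopper-Pearson) interval for 8/120 is 0.0292 to 0.1271, width 0.0979, which matches 0.098. With 60 subjects and 4 events the width would be 0.1435. The stated precision therefore takes all 120 outcomes as known.

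**Step 2: risk before exit.** Cumulative hazard H = −ln(0.92) = 0.0834. Risk in the first half of the window: h = 1 − exp(−H/2) = 0.0408.

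**Step 3: expected observed rate.**
- Unknowns counted as no VTE: r = (1 − c) × 0.08 + c × h.
- Event-free leavers dropped: r / [(1 − c) + c × h].

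| c | Unfollowed of 120 | Counted as no VTE | Expected VTEs missed | Shortfall ÷ 1.6 points | Event-free leavers dropped |
|---|---|---|---|---|---|
| 5% | 6 | 7.8% | 0.24 | 12% | 8.2% |
| 10% | 12 | 7.6% | 0.47 | 24% | 8.4% |
| 20% | 24 | 7.2% | 0.94 | 49% | 8.9% |

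If all leavers were dropped, with or without an event, the equal-risk assumption would leave the rate at 8.0%.

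**Step 4: sensitivity at c = 10%, unknowns as no VTE.** Exit a quarter of the way through gives 7.4%; three quarters, 7.8%. Leavers with twice the hazard, exit halfway and overall risk held at 8%, gives 7.3%.

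**Step 5: chance of an apparent meaningful drop when aspirin does nothing.** A rate below 6.4% means 7 or fewer VTEs in 120. With X binomial (120, p), P(X ≤ 7) is 25% at p = 0.08. With unknowns as no VTE it is 27%, 30% and 36% at c = 5%, 10% and 20%.

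**Step 6: bounds.** With 8 observed VTEs and two unknown outcomes, the rate runs from 8/120 = 6.7% to 10/120 = 8.3%, a span of 1.7 points. Dropping those two instead gives 8/118 = 6.8%, only 0.11 point above 8/120. The span is 6/120 = 5 points with 6 unknown and 12/120 = 10 points with 12.

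**The case against.** A reader might infer that the error runs one way, toward an apparent benefit of aspirin. The documents do not support that, for two reasons.

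- The downward direction needs unknowns to be scored as non-events. That fits an analysis of all enrolled subjects, but no section says it. Scoring an unknown as no VTE is arguably itself an imputation, which the plan rules out. Section 7.4 also defines evaluable subjects as those who receive chemotherapy until surgery, which gives some support to leaving others out, although Section 13 never uses that set. Dropping event-free leavers moves the rate up.
- The comparator is an earlier study whose follow-up and handling of leavers are not described, so the net effect on the comparison is unknown.

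The size can also be challenged. At an assumed 5% to 10% loss, under half a VTE is missed, the shift is 0.2 to 0.4 point, and the chance of a spurious drop is already 25% with perfect follow-up. Some exits may lose little: if disease progression ends chemotherapy and surgery is deferred, the window closes a week later, and some laboratory abnormalities qualify as AEs with continued collection. The DOAC option covers only subjects on study drug when the amendment was approved. Withdrawn subjects usually stay under their provider's care, so some VTEs could still be found.

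All of this stands as a limit on direction and size. It does not close the gap. The expectation of no loss in Section 10.5 does not address withdrawals that the protocol itself permits, and the follow-up mentioned in 6.6.2 for withdrawn subjects is standard care, not study data collection.

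**Conclusion.** The concern holds as an inconsistency between the analysis population and outcome collection, and it should be fixed. VTE status to the end of the window will be unknown for any subject who leaves by a route without follow-up, and no rule says how that subject counts. On the most natural reading, where such subjects stay in the denominator as non-events, the reported rate is a lower bound and is biased down. If event-free leavers are dropped, it is biased up.

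The size depends on withdrawal rates that the documents do not give. At the assumed 5% to 10% the shift is a small fraction of the 9.8-point interval; at 20% it reaches about half of the 1.6-point target in the downward case. No conclusion about a net bias in favor of aspirin against the historical 8% can be drawn from the documents.

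As a separate point, 6.6.2 says of withdrawn subjects that "subjects will not receive any other regimen", while Section 7.1 lets some come off study and begin a DOAC. These passages contradict each other and must be reconciled.

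**What to change.** 1. In Sections 3.3, 7.4, 10.5, 10.6 and 13.4, separate stopping aspirin from leaving data collection. Continue record-based VTE ascertainment to the end of the window in 8.7.2 after every type of exit (voluntary, investigator-initiated, DOAC switch), unless consent to record access is withdrawn. Widen the on-study definition in 7.4 to match.
2. Replace the term censored with wording such as: discontinued aspirin, VTE follow-up continues. State that any first VTE in the window counts for all enrolled subjects.
3. Report the number with unknown outcome by type of exit. Label the all-enrolled rate as counting unknowns as no VTE, that is, a lower bound, and give beside it the rate with all unknowns counted as VTE.
4. Separately, reconcile 6.6.2 with the DOAC option in 7.1.

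**Cost.** Protocol and SAP wording, a consent line on record access after withdrawal, and a little more chart review, since the same collection is already planned after AE and VTE exits. VTEs treated elsewhere may be missed, subjects already withdrawn may not be covered, and the upper bound is wide if many outcomes are unknown. Even then, the number unknown by exit type tells the reader how far to trust the rate.
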